7.10 Timepoints

Endpoints collected at the various visits and Day within visit will be labelled according to the Table below.

There will be a one-to-one association between the visit number and the timepoint used in the analysis.

Table 8: Timepoints Description

Timepoint	Label in Table
V1	Screening
V2 - Admission	Product Test
V2 – Day 1	Day 1
V2 – Day 2	Day 2
V3	Day 7
V4	Day 15
V5	Day 22

**Table 8: Timepoints Description**

Timepoint	Label in Table
V6 – Day 29	Day 29
V6 – Day 30	Day 30

8 SAMPLE SIZE JUSTIFICATION

A total of 60 subjects will be enrolled randomized with a 1:1 randomization ratio (~30 subjects randomized to P3P-1mg and ~30 to P3P-2mg). The sample size is empirically based.

9 CHANGES FROM THE PROTOCOL SPECIFIED STATISTICAL ANALYSIS

The following changes with respect to the analysis populations were made in the SAP compared to the Protocol:

- Changes regarding Population of Subjects to be Used for Different Endpoints

Endpoints	Protocol	SAP
Pharmacodynamics (VAS craving, Sensory questionnaire, ABOUT™ -Product Experience)	PK	Randomized
Product Acceptance	PK	Randomized
Puffing Inhalation Behavior	PK	Randomized

In addition, results for the 2 variants combined will not be reported except for data collected at baseline.

- Changes regarding Analysis Model for PK and AUC for VAS craving score

In the protocol, an ANOVA model with sex and product exposure category as factors was anticipated to be used to compare PK parameters and AUC for VAS craving score between variants at Day 30. The ANOVA model was replaced by an ANCOVA model with sex and product exposure category as factors and Day 1 value as covariate.

No Day 1 comparisons will be performed. Within-group comparisons Day 30 versus Day 1 will also be performed in an ANOVA model with sex and product exposure category as factors.

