### 12.5.3 Statistical Analysis

PK parameters will be summarized as described in section 12.1.3.

Nicotine PK profiles will be summarized and plotted over time for each visit.

An analysis of variance (ANOVA) will be conducted for Day 1 and Day 30 on background-corrected  $AUC_{(0-4h)}$  and background-corrected  $C_{max}$  endpoints in the natural logarithmic scale. The model will include sex as a covariate. The results of this analysis for each of  $cAUC_{(0-4h)}$  and  $cC_{max}$  will be presented as geometric least square means and 95% confidence intervals for each variant and least square mean ratio and 95% confidence intervals of P3P-2mg:P3P-1mg ratio.

For the ANOVA tests, the following hypothesis will be tested:

$H_0: \mu_1 = \mu_2$

$H_1: \mu_1 \neq \mu_2$

where  $\mu_1$  and  $\mu_2$  are the means (arithmetic or geometric) for each product variant, respectively.

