12.1.7 Definitions of Product Exposure Categories

Product exposure categories will be created by calculating the average P3P consumption over the exposure period (from Day 1 to Day 29) as the total number of P3P consumables used during the exposure period / duration of the exposure period.

Subjects will be categorized according to their average P3P consumption in one of the 3 product exposure categories by variant (total of 6 subgroups):

- ≤ 5 P3P/Day

- >5-10 P3P/Day
- >10 P3P/Day

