12.5 Planned Statistical Analyses

12.5.1 Primary Analyses of PK parameters

An analysis of covariance (ANCOVA) will be conducted at Day 30 on background-corrected $AUC_{(0-4h)}$ ($cAUC_{(0-4h)}$) and background-corrected C_{max} (cC_{max}) endpoints in the natural logarithmic scale. The model will include sex and variant as factors and value at Day 1 in the natural logarithmic scale as a covariate. The results of this analysis for each of $cAUC_{(0-4h)}$ and cC_{max} will be presented as geometric least square means and 95% confidence intervals for each variant and least square mean ratio and 95% confidence intervals of P3P-2mg:P3P-1mg ratio.

The same ANCOVA analysis will be performed for the $AUC_{(0-4h)}$ and C_{max} derived using uncorrected concentrations.

LS means for each product will be back-transformed by exponentiation and will be tabulated together with the ratio (P3P-2mg:P3P-1mg) and 95% CI.

In addition, least square mean ratio and 95% confidence intervals of Day 30 versus Day 1 will be provided by variant using an ANOVA model for the difference Day 30 – Day 1 in the natural logarithmic scale endpoints; the ANOVA model will have variant and sex as factors. LS means for each product will be back-transformed by exponentiation.

The geometric CV will also be presented as $CV(\%) = 100\sqrt{(e^{MSE} - 1)}$, where MSE is the mean square error of the fitted model residual.

Descriptive statistics for t_{max} will be provided by P3P variant, the p-value resulting from the non-parametric between-group comparison (Wilcoxon Rank Sum Test) will be reported. The Hodges-Lehman estimate for the between-group difference in median will be reported together with its 95% CI.

Descriptive statistics will be presented by sex (male or female) and by product exposure category.

For t_{max} , descriptive statistics by sex and product exposure will also be provided.

To better understand the impact of the higher than expected T_0 values, a sensitivity analysis of the Background-Corrected and Uncorrected $AUC_{(0-4h)}$ and C_{max} will be performed where data for subjects with their T_0 value $>5\%$ of their C_{max} value will be excluded from the analysis.

The data will be presented in the below outputs:

TFL number	Title
TABLES	
15.2.9.1	Descriptive Statistics of Background-Corrected and Uncorrected Pharmacokinetic Parameters of Nicotine (AUC _(0-4h) and C _{max}) at Day 1 and Day 30 – PK Population

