12.5.2 Secondary Analyses

12.5.2.1 VAS Craving score

At Day 30, an analysis of covariance (ANCOVA) will be performed on the AUC for the VAS craving score over the duration 0-4h post T₀ denoted AUC_{VAS Craving (0-4h)}. The model will have P3P variant and sex as factors and Day 1 value as covariate. Comparisons between variants will be performed and LSmeans differences between variant reported with their 95% CI. LSMeans and 95% CI for the AUC_{VAS Craving (0-4h)} by variant will also be reported.

Changes from baseline at Day 30 in AUC_{VAS Craving (0-4h)} will also be analyzed in an ANOVA model with variant and sex as factors. Within-group changes from baseline will be estimated using LSMeans and 95% CI.

Descriptive Statistics of AUC_{VAS Craving (0-4h)} at Day 1 and Day 30 and Change from Day 1 at Day 30 Overall; By Sex and By Exposure Category will be provided.

VAS craving score at Day 1 and Day 30 and changes from Day 1 value will be summarized in a descriptive manner by timepoint and P3P variant.

TFL number	Title
TABLES	
15.2.13.1	Descriptive Statistics of AUC _{VAS Craving (0-4h)} at Day 1 and Day 30 and Change from Day 1 at Day 30 – Randomized Population
15.2.13.2	Analysis of AUC _{VAS Craving (0-4h)} at Day 1 and Day 30 and Change from Day 1 at Day 30 – Randomized Population
15.2.13.3	Descriptive Statistics of AUC _{VAS Craving (0-4h)} at Day 1 and Day 30 and Change from Day 1 at Day 30 – By Sex - Randomized Population
15.2.13.4	Descriptive Statistics of AUC _{VAS Craving (0-4h)} at Day 1 and Day 30 and Change from Day 1 at Day 30 – By Product Exposure Category - Randomized Population
15.2.13.5	Descriptive Statistics of VAS craving score at Day 1 and Day 30 and Change from Day 1 at Day 30 by Timepoint – Randomized Population
15.2.13.6	Descriptive Statistics of VAS craving score at Day 1 and Day 30 and Change from Day 1 at Day 30 by Timepoint by Sex – Randomized Population
15.2.13.7	Descriptive Statistics of VAS craving score at Day 1 and Day 30 and Change from Day 1 at Day 30 by Timepoint by Product Exposure Category – Randomized Population
FIGURES	
15.3.3.1	VAS Craving Score Profiles By Timepoint at Day 1 and Day 30 – Randomized Population
15.3.3.2	Individual VAS profiles – Randomized Population

TFL number	Title
LISTINGS	
15.1.13.1	Listing of AUCVAS Craving (0-4h)
15.1.13.2	Listing of VAS craving scores

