12.5.2.3 ABOUTTM-Product Experience Questionnaire

The questionnaire which consists of multi-item scales and two single-item scales will be listed and summarized by variant and by stratification factor (sex) for the PK populations.

At Day 30, an ANCOVA model will be used to estimate the mean P3P-2mg:P3P-1mg difference by subscale of the ABOUTTM-Product Experience Questionnaire; the model will include P3P variant and sex as factors and value of the subscale score at Day 1 as covariate.

LS means for each variant with 95% interval estimate will be presented in the tables together with the LS mean between-variant difference and 95% confidence interval.

Within-group comparisons between Day 30 and Day 1 will be performed on the basis of an ANOVA model with sex and product exposure category as factors.

The data will be presented in the below outputs:

TFL number	Title
TABLES	
15.2.15.1	Descriptive Statistics of ABOUT™-Product Experience Questionnaire Subscales at Day 1 and Day 30 and Change from Day 1 at Day 30 - Randomized Population
15.2.15.2	Analysis of ABOUT™ Product Experience Questionnaire Subscales at Day 30 and Change from Day 1 at Day 30 - Randomized Population
15.2.15.3	Descriptive Statistics of ABOUT™ Product Experience Questionnaire Subscales at Day 1 and Day 30 and Change From Day 1 at Day 30 by Sex – Randomized Population
15.2.15.4	Descriptive Statistics of ABOUT™ Product Experience Questionnaire Subscales at Day 1 and Day 30 and Change From Day 1 at Day 30 by Product Exposure Category – Randomized Population
15.2.15.5	Descriptive Statistics of ABOUT™ Product Experience Questionnaire Individual Questions at Day 1 and Day 30 and Change from Day 1 at Day 30 – Randomized Population
LISTINGS	
15.1.15.1	Listing of ABOUT™ Product Experience Questionnaire Results

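### SAP 9, and the within-group model in SAP 12.5.2.3, adjust for P3P use after randomization where the parallel models in SAP 12.5.1 and 12.5.2.1 use variant and sex

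*SAP*

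**What the plan says.** SAP 9 records changes from the protocol. It says that the protocol anticipated a model with sex and product exposure category for the PK parameters and the craving AUC, and then: "The ANOVA model was replaced by an ANCOVA model with sex and product exposure category as factors and Day 1 value as covariate". It continues: "Within-group comparisons Day 30 versus Day 1 will also be performed in an ANOVA model with sex and product exposure category as factors". Neither list names variant, although the same paragraph describes the Day 30 analysis as a comparison of the variants.

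The analysis sections differ. For the Day 30 PK model, SAP 12.5.1 says: "The model will include sex and variant as factors and value at Day 1 in the natural logarithmic scale as a covariate". For Day 30 minus Day 1 it says: "the ANOVA model will have variant and sex as factors". For the craving AUC at Day 30, SAP 12.5.2.1 says: "The model will have P3P variant and sex as factors and Day 1 value as covariate", and its change model also has variant and sex.

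The protocol model, in Protocol 12.5.3, is: "The model will include sex as a covariate".

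For the ABOUT-Product Experience subscales, SAP 12.5.2.3 uses variant, sex and the Day 1 score at Day 30. The within-group comparisons, however, "will be performed on the basis of an ANOVA model with sex and product exposure category as factors".

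SAP 12.1.7 forms the categories by "calculating the average P3P consumption over the exposure period (from Day 1 to Day 29"). There are three use levels per variant, six subgroups in all.

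**The concern.** Randomization takes place on Day -1. All the use that defines the category comes later and is chosen by the subject, up to 15 products a day. A subject on the weaker product may take more units, and a subject who dislikes the assigned variant may take fewer. The category may therefore be partly a result of the assignment. A model that holds it fixed compares subgroups that randomization did not make alike.

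Three things are at stake. The primary PK model has two descriptions in one SAP, with no statement of which prevails. The formal record of departures from the protocol misdescribes the protocol's model. For the product experience subscales, the category model is the only within-group rule given, so no other section corrects it.

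**Working it through.** The plan states no effect size, SD or power, so there is no figure of its own to reproduce. The check sets the models side by side and then illustrates what the category does.

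**Model terms**

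| Analysis | SAP 9 | SAP 12.5 | Protocol |
|---|---|---|---|
| PK, Day 30 | sex, category, Day 1 | 12.5.1: variant, sex, log Day 1 | 12.5.3: sex |
| PK, Day 30 vs Day 1 | sex, category | 12.5.1: variant, sex | no model |
| Craving AUC, Day 30 | sex, category, Day 1 | 12.5.2.1: variant, sex, Day 1 | 12.6.2: as 12.5.3 |
| Craving AUC, change | sex, category | 12.5.2.1: variant, sex | no model |
| Product experience, Day 30 | not covered | 12.5.2.3: variant, sex, Day 1 | no model |
| Product experience, change | not covered | 12.5.2.3: sex, category | no model |

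SAP 9 conflicts with section 12.5 in the first four rows. The last row stands alone: it differs from the Day 30 model in its own section and from the change models in 12.5.1 and 12.5.2.1.

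**Mean change in one arm**

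Take 30 subjects (SAP 8 gives about 30 per arm). Assume 18, 9 and 3 of them at the three use levels, with mean changes of 0.2, 0.6 and 1.0.

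- Arm mean: (18×0.2 + 9×0.6 + 3×1.0)/30 = 12.0/30 = 0.40.
- Equally weighted mean over categories: (0.2 + 0.6 + 1.0)/3 = 0.60.
- SE ratio, with a common SD: √[(1/9)(1/18 + 1/9 + 1/3)] / √(1/30) = 0.236/0.183 = 1.29.

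With 24/4/2 subjects the arm mean is 9.2/30 = 0.31, against 0.60, and the SE ratio is 1.62. Weighting by the observed numbers would restore 0.40 and 0.31. The SAP does not state the weights.

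**Variant comparison**

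An illustrative simulation used 60 subjects (30 per arm) and 4,000 runs. The assumptions are a direct 2mg:1mg ratio of 2.0, mean use of 8 per day on 1 mg, and log Day 30 PK rising by 0.05 per extra product per day. One unmeasured trait raises both use and Day 30 PK. The total Day 30 ratio is then 2 × exp(0.05 × shift in daily use on 2 mg), which is 1.81, 2.00 and 2.21 for shifts of −2, 0 and +2.

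| Shift | variant + sex | + category | variant + sex + Day 1 | + category |
|---|---|---|---|---|
| −2 | 1.81 | 2.13 | 1.16 | 1.37 |
| 0 | 2.00 | 2.00 | 1.29 | 1.29 |
| +2 | 2.20 | 1.88 | 1.42 | 1.21 |

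Without the category, the variant and sex model returns the total ratio. With the category, and without Day 1, it returns neither the total ratio nor the direct 2.0, because the trait is still confounded with variant within use levels. When use was made unrelated to PK, with a shift of −2, adding the category changed nothing (2.00 against 2.00).

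For Day 30 over Day 1, the variant and sex model gave 1.10 (1 mg) and 1.00 (2 mg) at a shift of −2. These match exp(0.1) = 1.11 and exp(0.1 − 0.1) = 1.00 to within rounding and simulation error.

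**The case against.** The best reply is that SAP 9 is only a summary. The section headed as the primary PK analysis gives the full model, outputs and table numbers, and a programmer would work from it. SAP 12.5.2.1 does the same for craving. This lowers the risk for those endpoints. It does not settle which text prevails, and it does not reach 12.5.2.3, where the category model is itself the operative text.

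A reader might infer that the SAP 9 models cannot give any result per variant. The documents do not support that. SAP 9 speaks of comparing variants and rules out combined-variant results except at baseline. Protocol 12.5.3 also names only sex while promising a 2mg:1mg ratio, so variant may be implied. The six-subgroup definition contains variant, and within-group models could be fitted arm by arm. What stands is that the lists name no variant term and that every one of these readings still conditions on use.

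A reader might also infer that an empty use category makes the estimates non-estimable. That holds for a contrast over a missing level of a six-level factor. It does not hold for an additive variant-plus-category model with one empty cell, and in an arm-wise fit the unused level drops out.

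Nor is exposure foreign to the protocol. Protocol 12.3 foresees analysis by actual product exposure and leaves the categories to the SAP. SAP 9 is therefore wrong about the model terms, but not about the protocol's interest in exposure.

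Finally, the study is descriptive, Protocol 12.1.5 sets no significance level, and SAP 12.1.6 says that no claim rests on individual intervals. That limits the consequences, but the intervals will still be read as estimates for the variants.

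**Conclusion.** The point holds in a bounded form. SAP 9 contradicts SAP 12.5.1 and 12.5.2.1 on the factors of four analyses and misstates the protocol model. In SAP 12.5.2.3 only the within-group change is affected. It would go too far to say that the Day 30 model there drops variant, or that this section contradicts 12.5.1, since it keeps variant at Day 30 and concerns another endpoint.

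These findings rest on the text alone. The size of any distortion does not. The step from 0.40 to 0.60 needs the assumed split, the assumed changes and equal weights, and should not be read as a forecast of a 50% error. The simulated shifts need use to be related to outcome; for the variant ratio they also need strength to change use. If use is unrelated to outcome, the distortion is nil.

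A reader might infer that adopting 12.5.1 throughout yields the total variant effect at Day 30. It does not: the Day 1 value is itself measured on the assigned product, and in the simulation with no shift in use a ratio of 2.00 became 1.29 after adjustment for it. That is a separate point, which this correction leaves open.

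**What to change.** In SAP 9, name variant and sex as the factors in both sentences on the SAP models, keeping the Day 1 covariate in the first. Correct the account of the protocol so that sex is the only adjusting term credited to Protocol 12.5.3. Mention Protocol 12.3 if the interest in exposure is to be recorded.

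In SAP 12.5.2.3, use variant and sex for the ANOVA of Day 30 minus Day 1, as in 12.5.1 and 12.5.2.1, and report the change per variant.

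Keep product exposure category for the stratified descriptive tables in SAP 12.1.1, which need no change.

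The cost is a few sentence edits. No data, visit or table shell has to be added. SAP 3 allows amendments before database lock; after that, the change belongs in the research study report.

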#### 12.1.5 Significance Level for Inferential Analysis

Not applicable.

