5 STUDY OBJECTIVES AND ENDPOINTS

5.1 Primary Objective and Endpoints

1. To assess nicotine pharmacokinetics following use of a single P3P-1mg or P3P-2mg product on Day 1 and Day 30.

Endpoints:

- Plasma nicotine time-concentration profile from prior product use to 4 hours post start of product use;
- PK parameters: maximum plasma concentration (C_{max}); time to maximum concentration (t_{max}); Area under the concentration-time curve from start of product use to 4 hours ($AUC_{(0-4h)}$).

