5.3 Study Hypotheses And Evaluation Criteria

5.3.1 Hypotheses

The study will be descriptive in nature. However, for the ANOVA tests, the following hypothesis will be tested:

$$H_0: \mu_1 = \mu_2$$

$$H_1: \mu_1 \neq \mu_2$$

where μ_1 and μ_2 are the means (arithmetic or geometric) for each product variant, respectively.

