15.2.9.2	Analysis of Background-Corrected and Uncorrected Pharmacokinetic Parameters of Nicotine (AUC _(0-4h) and C _{max}) at Day 30 and at Day 30 relative to Day 1 – PK Population
15.2.9.3	Descriptive Statistics of Background-Corrected and Uncorrected Pharmacokinetic Parameters of Nicotine (AUC _(0-4h) and C _{max}) at Day 1 and Day 30 by Sex – PK Population
15.2.9.4	Descriptive Statistics of Background-Corrected and Uncorrected Pharmacokinetic Parameters of Nicotine (AUC _(0-4h) and C _{max}) at Day 1 and Day 30 by Product Exposure Category – PK Population
15.2.10.1	Descriptive Statistics of Background-Corrected and Uncorrected t _{max} at Day 1 and Day 30 - PK Population
15.2.10.2	Analysis of Background-Corrected and Uncorrected t _{max} at Day 1 and Day 30 – PK Population
15.2.10.3	Descriptive Statistics of Background-Corrected and Uncorrected t _{max} at Day 1 and Day 30 – by Sex - PK Population
15.2.10.4	Descriptive Statistics of Background-Corrected and Uncorrected t _{max} at Day 1 and Day 30 – By Product Exposure Category – PK Population
15.2.11.1	Sensitivity Analysis of Background-Corrected and Uncorrected Pharmacokinetic Parameter of Nicotine (AUC _(0-4h) and C _{max}) at Day 1 and Day 30 – PK Population
FIGURES	
15.3.1.1	Pharmacokinetic Parameters of Nicotine By P3P variant – PK Population
LISTINGS	
15.1.9.1	Listing of Background-Corrected Pharmacokinetic Parameters of Nicotine – PK Population
15.1.10.1	Listing of Background- Uncorrected Pharmacokinetic Parameters of Nicotine – PK Population

Pharmacokinetic Profiles

Geometric mean (95% CI) profiles, spaghetti plots of individual PK profiles for each subject will also be presented by timepoint.

For the analysis and graphical presentation of plasma concentrations, the nominal timepoints will be used. Plasma concentration data will also be listed along with the details of the actual collection times.

TFL number	Title
TABLES	
15.2.12.1	Descriptive Statistics of Background-Corrected Plasma Nicotine Concentration at Day 1 and Day 30 by Timepoint– PK Population
15.2.12.2	Descriptive Statistics of Uncorrected Plasma Nicotine Concentration at Day 1 and Day 30 by Timepoint– PK Population
15.2.12.3	Descriptive Statistics of Background-Corrected Plasma Nicotine Concentration at Day 1 and Day 30 by Timepoint by Sex – PK Population
15.2.12.4	Descriptive Statistics of Background-Corrected Plasma Nicotine Concentration at Day 1 and Day 30 by Timepoint by Product Exposure Category – PK Population

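### SAP section 9 drops the protocol's Day 1 comparison of the two variants without a reason and misdescribes the protocol model, so no Day 1 ratio or difference is planned for cAUC(0-4h), cCmax or craving AUC

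*SAP*

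**What the plan says.** Protocol 12.5.3 sets out the primary analysis: "An analysis of variance (ANOVA) will be conducted for Day 1 and Day 30 on background-corrected" AUC(0-4h) and Cmax, on the log scale with sex in the model, reported as geometric LS means per variant and the 2mg:1mg ratio with 95% CI. Protocol 12.6.2 applies the same approach on both days to VAS craving on the linear scale, with LS mean differences.

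The SAP keeps the objective in 5.1, "To assess nicotine pharmacokinetics following use of a single P3P-1mg or P3P-2mg product on Day 1 and Day 30", and the hypothesis of equal variant means in 5.3.1. Section 9 then says "No Day 1 comparisons will be performed" for the PK parameters and craving AUC. SAP 12.5.1 follows this: "An analysis of covariance (ANCOVA) will be conducted at Day 30 on background-corrected" AUC(0-4h) and Cmax, with variant and sex as factors and the "value at Day 1 in the natural logarithmic scale as a covariate", plus a Day 30 to Day 1 ratio within each variant. SAP 12.5.2.1 has the matching structure for craving AUC.

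Several table titles still name Day 1: 15.2.10.2 (analysis of tmax), 15.2.11.1 ("Sensitivity Analysis of Background-Corrected and Uncorrected Pharmacokinetic Parameter of Nicotine") and 15.2.13.2 (analysis of craving AUC).

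**The concern.** A comparison that the protocol specifies for its primary PK endpoints has been removed, and the section that records the change gives no reason. The same section misstates the protocol. It says that the protocol anticipated a between-variant model at Day 30 with sex and product exposure category as factors. Someone reading only that section would not learn that the protocol had planned a Day 1 contrast.

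The contrast has value. From check-in on Day -1 subjects are confined without cigarettes (Protocol 6.2.1), they are randomized that day, and the next morning each uses one product under supervision after at least 10 hours of abstinence. Day 30 comes after an ambulatory period in which cigarette use does not lead to discontinuation (Protocol 6.2.3) and dropouts after randomization are not replaced (Protocol 5.2). Day 1 is therefore the randomized comparison of nicotine exposure least disturbed by attrition and dual use.

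**Working it through.** **Step 1. The passages side by side.**

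| | Protocol 12.5.3, 12.6.2 | SAP 9: account of the protocol | SAP 9: the replacement | SAP 12.5.1, 12.5.2.1 |
|---|---|---|---|---|
| Days compared between variants | Day 1 and Day 30 | Day 30 | Day 30 | Day 30 |
| Terms besides variant | sex | sex, exposure category | sex, exposure category, Day 1 value | sex, Day 1 value |

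Section 9 thus disagrees with the protocol on days and factors, and with SAP 12.5.1 on the exposure-category factor.

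**Step 2. What is still reported at Day 1.** SAP 12.1.3 and Table 15.2.9.1 give the geometric mean, its 95% CI and the geometric CV per variant for the PK parameters. Table 15.2.13.1 describes craving AUC. For tmax, SAP 12.5.1 plans a Wilcoxon test and a Hodges-Lehmann difference with 95% CI without naming a day, and Table 15.2.10.2 lists Day 1 and Day 30. No Day 1 ratio or difference is described for cAUC(0-4h), cCmax or craving AUC.

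**Step 3. Precision of the dropped ratio.** The plan has no figure to reproduce: the sample size of 60 (about 30 per arm) is called empirical, and no CV, effect size or power is stated. For a log-scale model with variant and sex:

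- s = sqrt(ln(1 + CV²))
- CI factor = exp( t(0.975, 2n − 3) × s × sqrt(2/n) )

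The CV is an assumption, shown as a range. At n = 30 there are 57 df, t is about 2.00 and sqrt(2/30) = 0.258.

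| Assumed CV | s | CI factor, n = 30 | 95% CI if the estimated ratio is 2.0 |
|---|---|---|---|
| 60% | 0.555 | 1.33 | 1.50 to 2.66 |
| 80% | 0.703 | 1.44 | 1.39 to 2.88 |
| 100% | 0.833 | 1.54 | 1.30 to 3.08 |

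If, for illustration, 24 per arm remained at Day 30, an unadjusted comparison there would have factors 1.38, 1.51 and 1.62.

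**Step 4. Is that precise enough to be useful?** Protocol 2.1.2 reports Cmax of 1.1 ng/mL for the 1 mg variant and 2.1 to 3.1 ng/mL for the 2 mg variants in the earlier PK study. The ratios are 2.1/1.1 = 1.91 and 3.1/1.1 = 2.82. At 1.91, power with 30 per arm (two-sided 0.05 assumed, normal approximation) is 0.995, 0.945 and 0.853 for CVs of 60, 80 and 100%.

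**Step 5. Does the Day 30 ANCOVA stand in for it?** The Day 1 covariate is measured on the randomized variant. If the true ratio R is the same on both days, with equal variances and within-arm correlation ρ, the ANCOVA's expected ratio is R^(1−ρ). For R = 2.0 and assumed ρ of 0.3, 0.5 and 0.7 this is 1.62, 1.41 and 1.23, and simulation agreed. The ANCOVA therefore does not supply the unconditional ratio that the Day 1 model would give.

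**The case against.** The best defence is that little is lost. The objective is to assess PK on two days, not to compare variants on each. The SAP says "The study will be descriptive in nature. However, for the ANOVA tests, the following hypothesis will be tested", and the hypothesis names no day and is still addressed at Day 30. The protocol section headed "Significance Level for Inferential Analysis" is marked not applicable, and SAP 12.1.6 rests no claim on individual intervals. The stated purpose is adaptation between baseline and one month, which the added Day 30 to Day 1 ratio serves directly. The deletion is declared in the section meant for changes. A reader can also derive an unadjusted Day 1 ratio and CI from the geometric means, CVs and numbers of subjects.

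Most of this stands, and it limits the point. A reader might infer that half of the primary objective has been abandoned; the retained Day 1 summaries show otherwise. A reader might infer that the Day 1 sensitivity table has nothing to support; it can support the Day 1 summaries and the Day 30 to Day 1 ratios. The title of Table 15.2.13.2 also covers change from Day 1, so it is weak evidence of a planned Day 1 test. Only the tmax table clearly conflicts with section 9.

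Nor is Day 1 wholly free of later events. Under SAP 7.1 a positive Day 1 slope borrows the Day 30 slope, and without a usable one the corrected parameters are not calculated. Under SAP 10.4 and 11.1 later major deviations, such as a missed visit, can remove a subject from the PK population. Earlier smoking and the Day -1 test of both variants also leave residual nicotine, although randomization makes that noise rather than bias between arms.

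The defence does not supply a reason for the change, a correct account of the protocol, or the sex-adjusted Day 1 estimate that the protocol specified.

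**Conclusion.** The concern holds in a limited form. The SAP removes, without explanation, a protocol-specified randomized comparison at Day 1 for cAUC(0-4h), cCmax and craving AUC, misdescribes the protocol model, and is inconsistent with its own tmax analysis. The missing PK contrast would have a 95% CI factor of 1.33 to 1.54, given about 30 evaluable subjects per arm and a CV of 60-100%; neither is guaranteed by the documents. The figure describes the precision forgone, not an error in a result that will be reported.

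A reader might also suspect that the deletion was prompted by data, because SAP 12.5.1 mentions higher than expected T0 values and sponsor and CRO staff are unblinded. Nothing in the documents links either to the Day 1 decision, and the SAP is to be final before database lock. For a study called descriptive, with Day 1 summaries retained, this is something that should be fixed rather than a fatal defect.

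**What to change.** 1. Delete "No Day 1 comparisons will be performed" from SAP section 9.
2. In SAP 12.5.1 add a Day 1 ANOVA of ln cAUC(0-4h) and ln cCmax on variant and sex, with the 2mg:1mg ratio and 95% CI in Table 15.2.9.2. Exposure category does not belong in this model, since SAP 12.1.7 derives it from consumption over Day 1 to Day 29.
3. In SAP 12.5.2.1 add the Day 1 LS mean difference between variants in craving AUC, with 95% CI, to Table 15.2.13.2.
4. Correct section 9's description of the protocol model to Day 1 and Day 30 with sex only, and reconcile its exposure-category factor with 12.5.1.
5. State the day or days of the tmax comparison, and align the titles of Tables 15.2.10.2, 15.2.11.1 and 15.2.13.2 with the text.

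The cost is a short SAP amendment and three further model fits on data the study already plans to collect. SAP section 3 allows title changes without an amendment, but the model text needs one.
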